# Clinical Study Protocol

## Johnson & Johnson Vision

The sample size estimates for primary endpoints were calculated using 1-sided Type I error rate of 0.025 for each endpoint. The sample size estimates for the two secondary endpoints were adjusted using a Bonferroni adjustment and calculated using a one-sided Type I error rate of 0.0125 (i.e., one-sided 0.025/2).

While no Toric wearers were enrolled in Phase 1, it is anticipated that the multifocal group would require the largest sample due to simultaneous optics of the multifocal lens and the intraocular scattering that naturally occurs with age, which can both compromise and reduce the quality of vision. Hence it is expected that the sample size required to test endpoints for Toric wearers would be no more than the sample size required for Multifocal wearers. As these endpoints did not have data from Phase 1, all hypotheses for the Toric wearers will be exploratory endpoints.

Table 9 displays the statistical power and associated sample sizes estimates derived for the primary and secondary endpoints for Sphere and Multifocal groups, given the assumed treatment effect sizes. Based on the table below, it is planned that Phase 2 will enroll approximately 135 subjects (45 subjects per group) with the target of 120 subjects (40 subjects per group) to complete the study, assuming approximately a 10% drop-out rate.

Table 9: Assumptions for Power and Sample Size Calculations for The Primary and Secondary Endpoints

Endpoint Type	Endpoint (Subject Group)	Standard Deviation of Paired Differences	Effect Size	Alpha	Power	Sample Size Per Group
Primary	Visual Range (Sphere)	0.10	1.83	0.05	0.94	6
	Visual Range (Multifocal)	0.23	0.52	0.05	0.90	41
Secondary	Motion Detection (Sphere)	1.16	0.99	0.03	0.92	16
	Brightness Perception (Multifocal)	0.20	0.70	0.03	0.91	29

### 14.3. Analysis Populations

#### Safety Population:

All subjects who are administered any test article excluding subjects who drop out prior to administering any test article.

#### Per-Protocol (PP) Population:

All subjects who successfully complete all visits and do not substantially deviate from the protocol as determined by the trial cohort review committee prior to database hard lock. Justification for the exclusion of subjects with protocol deviations from the per-protocol population set will be documented in a memo to file.

#### Intent-To-Treat (ITT Population):

All randomized subjects regardless of actual treatment and subsequent withdrawal from the study or deviation from the protocol.

# Clinical Study Protocol

## Johnson & Johnson Vision

### 14.4. Level of Statistical Significance

Although the Test and Control lenses are senofilcon A based lenses with and without the new UV/HEV filter, respectively, the study lenses assigned to each subject group will be different with different optical designs specifically for vision correction of the sphere, multifocal, and toric (astigmatism) lens wearers. Therefore, the planned hypotheses in Phase 2 will be tested separately for each subject group without Type I error adjustment across the three subject groups, due to different optical designs of the study lenses for different groups. The primary hypothesis for each subject group will be tested using a one-sided Type I error rate of 0.025. The secondary hypotheses will be tested only when the primary hypothesis is met for the same subject group. For secondary hypotheses, the Type I error rate will be adjusted using the Bonferroni approach for the two secondary hypotheses and each secondary hypothesis will be tested using the Bonferroni adjusted one-sided Type I error rate 0.0125 (i.e., one-sided 0.025/2).

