**Clinical Study Protocol**  
**Johnson & Johnson Vision**

**Secondary Hypotheses - Phase 2**

1. Subjects wearing the Test lens will have statistically significantly improved motion detection than the Control lens among spherical wearers.
2. Subjects wearing the Test lens will perceive an image statistically significantly brighter than the Control lens among multifocal wearers.

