### **14.2. Sample Size Justification**

Sample size for Phase 1 was not determined on the basis of statistical considerations because it is primarily for the collecting clinical data to calculate the required sample size for Phase 2.

Sample size requirements for Phase 2 were based on assumptions derived from the analysis of selected data collected in Phase 1. It was calculated that the total sample size of 120 subjects to complete (40 per group) the study provides at least 90% power to test each primary and secondary hypothesis. The sample size and power calculations were performed using a paired sample *t*-test approach (exact method) in PASS (NCSS, 2021).

A gate-keeping approach will be used to control the study-wise Type I error rate at the one-sided 0.025 level and adjust for multiplicity due to multiple efficacy endpoints of interest in combination of Bonferroni adjustment. The null hypothesis for the primary efficacy endpoints has to be rejected at one-sided alpha level of 0.025 first, in order to propagate the full alpha to the secondary family of hypothesis tests. The Bonferroni approach will apply then to testing the secondary efficacy endpoints.

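### Sections 14.2 and 14.4 state incompatible multiplicity schemes: the study-wise control claimed is not delivered, and the gate for the secondaries is left open to two readings

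*Combined protocol and SAP*

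**What the plan says.** - **Section 14.2** describes gatekeeping combined with Bonferroni, meant to hold the study-wise error at one-sided 0.025. Its gate reads "The null hypothesis for the primary efficacy endpoints has to be rejected at one-sided alpha level of 0.025 first". The full alpha then passes to a secondary family, which is split by Bonferroni. Both secondaries are sized at one-sided 0.0125.
- **Section 14.4** says "the planned hypotheses in Phase 2 will be tested separately for each subject group without Type I error adjustment across the three subject groups", and gives the different optical designs as the reason. It adds "The primary hypothesis for each subject group will be tested using a one-sided Type I error rate of 0.025" and "The secondary hypotheses will be tested only when the primary hypothesis is met for the same subject group". It then says "For secondary hypotheses, the Type I error rate will be adjusted using the Bonferroni approach for the two secondary hypotheses", which puts each at 0.0125.
- **Secondary hypotheses for Phase 2 (Section 2).** There are two. The one for spherical wearers is "Subjects wearing the Test lens will have statistically significantly improved motion detection than the Control lens among spherical wearers". The one for multifocal wearers is brightness perception. Section 14.2 makes all toric hypotheses exploratory.
- **Section 14.6** tests both secondaries with adjusted one-sided limits but gives no numeric level.

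**The concern.** A multiplicity plan must settle two things: the family over which error is controlled, and the condition under which each secondary may be tested. The two sections answer both differently. For 14.2 the family is the study, and the gate is most naturally both primaries. For 14.4 the family is the subject group, and the gate is that group's primary. The division by two in 14.4 is itself an adjustment across groups, which the same paragraph says will not be made.

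Section 2.1 says the results may be used to support marketing claims. Whether a secondary may be claimed when only one primary succeeds should therefore be fixed before anyone sees unmasked data.

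**Working it through.** **1. Reproduce Table 9.** The method is the exact paired t-test named in 14.2: power = P(T > t(1−α, n−1)), where T is noncentral t with n−1 df and noncentrality d√n. The inputs d and n are from Table 9.

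| Endpoint (group) | d | n | one-sided α | computed | stated |
|---|---|---|---|---|---|
| Visual range (sphere) | 1.83 | 6 | 0.025 | 0.943 | 0.94 |
| Visual range (multifocal) | 0.52 | 41 | 0.025 | 0.901 | 0.90 |
| Motion (sphere) | 0.99 | 16 | 0.0125 | 0.916 | 0.92 |
| Brightness (multifocal) | 0.70 | 29 | 0.0125 | 0.912 | 0.91 |

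The table's alpha entries of 0.05 and 0.03 fit as two-sided equivalents (0.05, and 0.025 rounded). At one-sided 0.025 the secondaries would give 0.959 and 0.953, so Table 9 was built with the halved level.

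**2. Level needed under 14.4's per-group rule.** Each group has one secondary, so Bonferroni gives 0.025/1 = 0.025. Testing the primary and then one secondary, each at 0.025, is a fixed sequence that holds 0.025 in that group.

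**3. Study-wise error under 14.4's rule.** Two primaries are each tested at 0.025 in different subjects, with both nulls true:

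1 − (1 − 0.025)² = 0.0494.

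Without independence the bound is 0.05. Same-group gates add nothing here, because a secondary can be rejected only after its own primary. Gating the secondaries on both primaries would not lower the figure either, since the error comes from the primaries themselves.

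**4. When the gates disagree.** At 40 completers, multifocal visual range (d = 0.52, α = 0.025) has power 0.894, so it fails with probability 1 − 0.894 = 0.106. Sphere visual range has power of about 1.000. In that 11% or so, 14.4 tests sphere motion, and 14.2, read as requiring both primaries, does not.

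**5. What the halving buys.** Suppose both primaries work as planned and both secondary nulls are true. Use same-group gates, independent groups, and independent tests within the multifocal group. The chance of at least one false secondary claim is:

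- at 0.0125 each: 1 − (1 − 0.0125)(1 − 0.894 × 0.0125) = 0.0235
- at 0.025 each: 1 − (1 − 0.025)(1 − 0.894 × 0.025) = 0.0468

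With both gates certain to open, the figures are 0.0248 and 0.0494.

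**6. What the halving costs at 40 completers.**

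| Endpoint | share of planned effect | power at 0.0125 | power at 0.025 |
|---|---|---|---|
| Brightness | 100% | 0.979 | 0.991 |
| Brightness | 60% | 0.629 | 0.736 |
| Motion | 100% | 0.9999 | 1.000 |
| Motion | 60% | 0.918 | 0.956 |

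The 60% rows are an assumption, not a scenario in the plan. On 39 df the critical values are 2.331 and 2.023, so limits at the halved level sit about 15% further from the estimate. This takes 98.75% as the level behind 14.6's adjusted limits.

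**The case against.** The halving has a stated purpose. Section 14.2 asks for study-wise control, passes alpha to a single secondary family and splits it. Table 9 is sized that way, 14.6 uses adjusted limits, and 14.4's own last sentence agrees. On this view the odd part is 14.4's clause disclaiming adjustment. The version 5.0 entry in the change history lists 14.2, 14.5, 14.6 and 14.7 as updated but not 14.4, which suggests, without proving, that 14.4 was not refreshed. A stricter level for a secondary is also always permissible: within each group the error stays at or below 0.025. Finally, 14.2's gate sentence pairs a singular null hypothesis with plural endpoints and never says outright that both must be rejected.

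All of this stands, and it limits the point. A reader might infer that the division by two is a mistake to be deleted, or that it costs the secondaries material power. The documents support neither. It is conservative, it fits 14.2, Table 9 and 14.6, and both secondaries keep well over the 90% power that 14.2 seeks at the planned effects. Removing it about doubles the chance of a false secondary claim across groups. A reader might also take 14.2 as plainly demanding both primaries. That is the most natural reading and the one its study-wise claim points to, but the sentence is loose.

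None of this rescues the study-wise claim. Two primaries at 0.025 each, claimed separately, exceed 0.025 whichever gate is meant for the secondaries.

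**Conclusion.** The point holds as a conflict between two sections, not as a failure of any single test. Each group's own tests remain valid at one-sided 0.025. Two things are wrong:

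- The study-wise control claimed in 14.2 is not delivered under 14.4's rule: about 0.049 against 0.025, with both primary nulls true and independent groups.
- The two sections can give different answers on sphere motion when multifocal visual range fails, about 11% of the time.

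The 11% rests on Table 9's effect size, 40 completers and the paired t-test. The planned mixed model would differ only trivially in degrees of freedom. The power cost of the halving is minor: 1.1 points for brightness at the planned effect and almost nothing for motion. It is not the reason to act.

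**What to change.** Adopt one scheme in 14.2, 14.4 and 14.6 before unmasking.

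**(a) Per-group control.** Remove the study-wise claim from 14.2 and replace its gate sentence with 14.4's same-group gate. Test each secondary at one-sided 0.025 with 97.5% one-sided limits. Keeping 0.0125 would be valid but conservative, and should then be described as a choice. The cost of moving to 0.025 is that the chance of at least one false secondary claim across groups goes from about 0.024 to 0.047 when both primaries work.

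**(b) Study-wise control.** Remove 14.4's disclaimer of adjustment and its same-group gate. Keep the secondaries at 0.0125 and state 98.75% one-sided limits in 14.6. Then handle the primaries in one of two ways:

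- Require both primaries to be rejected jointly before any claim, primary or secondary. This gives up a primary claim in one group alone. The chance that both succeed on Table 9's figures is about 1.000 × 0.894 = 0.894.
- Adjust the primaries. At 0.0125 each, multifocal visual range power at 40 completers falls from 0.894 to 0.827, and 90% power needs 49 completers.

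A both-primaries gate on the secondaries alone is not enough for (b), for the reason in step 3 of the working.

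Option (a) and the joint-claim form of (b) need only wording changes and no extra data. Adjusting the primaries costs power or subjects.

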### 14.5. Primary Analyses

#### Phase 1

There is no planned hypothesis testing in Phase 1. Data collected during Phase 1 of the study will be used to power Phase 2 for testing superiority of test lens relative to control lens with respect to the primary endpoint within each subject group. See section 14.8 for details regarding the interim analysis of the Phase 1 data.

#### Phase 2

##### Visual Range

The visual range metric will be analyzed separately for two of the three subject groups (i.e., Spherical wearers and Multifocal wearers) using a linear mixed model. The analysis will be conducted on the ITT population. An appropriate distribution from the exponential family (e.g., normal or lognormal) will be considered for the linear mixed modeling based on the distribution of the endpoint. The model will include lens type, lens sequence, and period as fixed effects. Other baseline and subject characteristics such as age, gender, race, and iris color will be included as fixed covariates when appropriate. An unstructured (UN) covariance matrix will be used to model the residual errors among within-subject repeated measures (R-side). If the model fails to converge, a Compound Symmetric (CS) matrix may be considered. The Kenward and Roger method will be used for the denominator degree of freedom.

##### Hypothesis Testing

The null and alternative hypotheses for testing superiority of the Test relative to the Control with respect to mean visual range within each subject group (Spherical wearers and Multifocal wearers) are as follows:

$$H_0: \mu_T - \mu_C \leq 0$$
$$H_A: \mu_T - \mu_C > 0$$

Where  $\mu_T$  and  $\mu_C$  represent mean visual range (i.e., LRE of simulated haze) for the Test and Control lenses, respectively. The one-sided confidence interval for the least-squares (LS) mean difference (Test – Control) and associated p-value will be calculated to test the primary

# Clinical Study Protocol

## Johnson & Johnson Vision

hypothesis for visual range. Superiority of the Test lens relative to the Control will be declared if the lower confidence limit is greater than 0.

If a significant sequence effect will be observed, only the period 1 data will be analyzed.

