#### Primary Objective(s)

The primary objective of Phase 1 study is to collect clinical data to estimate the required Phase 2 sample size for achieving the primary objective with adequate statistical power given the prespecified primary hypotheses testing.

The primary objective of the Phase 2 study is to objectively measure potential benefits of a new UV/HEV filter using psychophysical testing techniques.

The results from this study may be used to support marketing claims or help understand market readiness of the Test lenses that contain the UV/HEV filter.

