# **Clinical Study Protocol**

## **Johnson & Johnson Vision**

### **4.2. Study Design Rationale**

The purpose of this study is to evaluate the performance of a new UV/HEV-filter in a 2x2 crossover design for three different subject groups (i.e., sphere wears, multifocal wears, and toric wears). Crossover designs are a well-established study design in which subjects are exposed to multiple treatments during different time periods. This design is cost effective and more efficient since it eliminates part of the inter-subject variability from the treatment comparisons. Subjects will be randomized into the two lens wear sequences: Test/Control or Control/Test. Randomization eliminates selection bias and balances both the known and unknown confounding factors that may affect the study outcomes. A potential limitation of crossover design is the carry-over effect from the previous treatment. The 2 study periods (visits) will be separated by 1-14 days and the wearing time of 2.5-3 hours in each period is considered effectively short to minimize the presence of the carry-over effect in the psychometric tests of interest. Rest period between trials within a single measurement type and between different measurement types is incorporated to eliminate the impact of any previous testing.

- Within a single measurement type (e.g., visual range), a minimum of 30-seconds will be taken between trials.
- Between measurement types (e.g., when switching from visual range to measuring brightness perception), a 5-minute break will be taken.
- Participants will be given a 15-minute break after every 45 minutes of visual function testing.

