# **Clinical Study Protocol**

## **Johnson & Johnson Vision**

where  $\mu_T$  and  $\mu_C$  represent mean brightness perception (i.e., LRE) for the Test and Control lenses, respectively. The one-sided adjusted confidence interval for the LS mean difference (Test – Control) and associated p-value will be calculated to test statistical superiority. Superiority of the Test lens relative to the Control will be declared if the adjusted lower confidence limit is larger than 0.

If a significant sequence effect was observed, only the period 1 data will be analyzed for the corresponding endpoint.

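### Switching to period 1 data after a significant sequence test breaks the stated one-sided 0.025 level of the confirmatory lens comparison

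*Combined protocol and SAP*

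**What the plan says.** Section 14.5 fits a linear mixed model with lens, sequence and period to visual range, separately in sphere and multifocal wearers, and declares superiority from a one-sided confidence limit. It then adds: "If a significant sequence effect will be observed, only the period 1 data will be analyzed". Section 14.6 ends with the same rule for motion detection and brightness perception: "If a significant sequence effect was observed, only the period 1 data will be analyzed for the corresponding endpoint".

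Section 14.4 fixes the level: "The primary hypothesis for each subject group will be tested using a one-sided Type I error rate of 0.025". Each secondary test is set at one-sided 0.0125, and "The secondary hypotheses will be tested only when the primary hypothesis is met for the same subject group". Section 14.2 makes the wider claim: "A gate-keeping approach will be used to control the study-wise Type I error rate at the one-sided 0.025 level".

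No section gives the level at which the sequence effect counts as significant, or adjusts the period 1 test for having been selected. On carry-over, Section 4.2 relies on the design: the visits are separated by 1 to 14 days, and the wearing time of 2.5 to 3 hours "is considered effectively short to minimize the presence of the carry-over effect in the psychometric tests of interest".

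**The concern.** The rule makes the confirmatory analysis a two-stage procedure. The two-period test and the period 1 test are each valid on their own, but choosing between them with a sequence test on the same data is not.

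Without carry-over, a significant sequence effect means that one randomised group happened to score higher overall than the other. The period 1 comparison sets the same two groups against each other using half of the same measurements, so the trigger picks out the datasets in which the period 1 difference is already extreme.

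The synopsis labels the study Feasibility, but Phase 2 runs formal superiority tests with a claimed error rate, and Section 2.1 states: "The results from this study may be used to support marketing claims". At stake is a false-positive rate above the stated one for both primary tests and, behind them, both secondary tests.

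**Working it through.** **Inputs from the documents.** One-sided 0.025 per primary test and 0.0125 per secondary test (14.4); 40 completers per group (14.2); two randomised sequences (5.1); lens, sequence and period in the model (14.5); multifocal visual range effect size 0.52 in units of the paired-difference SD, power 0.90 at n = 41 (Table 9).

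**Assumptions, not in the documents.** 20 subjects per sequence; normal data; no covariates; within-subject correlation ρ from 0 to 0.9; two-sided sequence test at 5% or 10%; no carry-over unless stated.

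**1. The plan's own figure.** Paired t-test at one-sided 0.025, noncentrality 0.52 × √41 = 3.33 on 40 df: power 0.901, matching the stated 0.90. With 40 completers it is 0.894.

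**2. Why the tests are linked.** Let Y1 and Y2 be a subject's two period values, with equal variance. The sequence test compares the groups on Y1 + Y2, the two-period test on Y1 − Y2, and the period 1 test on Y1.
- Corr(Y1 + Y2, Y1 − Y2) = 0, so the trigger does not disturb the two-period test.
- Corr(Y1 + Y2, Y1) = √((1 + ρ)/2), which is 0.71 at ρ = 0, 0.87 at 0.5, 0.95 at 0.8 and 0.97 at 0.9. The trigger therefore strongly selects on the period 1 test.

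**3. Error of the combined rule.** With trigger level a, and c the rejection rate of a true null given a switch,

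error = (1 − a) × 0.025 + a × c.

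Simulated c is 0.165 (ρ = 0) to 0.386 (ρ = 0.9) for a 5% trigger, and 0.125 to 0.238 for a 10% trigger. Hence:
- 5%, ρ = 0: 0.95 × 0.025 + 0.05 × 0.165 = 0.0320
- 5%, ρ = 0.9: 0.95 × 0.025 + 0.05 × 0.386 = 0.0431
- 10%, ρ = 0: 0.90 × 0.025 + 0.10 × 0.125 = 0.0350
- 10%, ρ = 0.9: 0.90 × 0.025 + 0.10 × 0.238 = 0.0463

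**4. Direct simulation** (400,000 trials per setting, simulation standard error about 0.0003), one-sided error at nominal 0.025:

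| ρ | 0 | 0.3 | 0.5 | 0.7 | 0.8 | 0.9 |
|---|---|---|---|---|---|---|
| 5% trigger | 0.0318 | 0.0342 | 0.0368 | 0.0386 | 0.0409 | 0.0432 |
| 10% trigger | 0.0348 | 0.0376 | 0.0409 | 0.0429 | 0.0451 | 0.0466 |

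The two-period test alone gives 0.0243 to 0.0251. A 1% trigger gives 0.027 to 0.030 and a 20% trigger 0.037 to 0.045. With 22 per sequence, close to the 45 enrolled, the 5% and 10% triggers give 0.032 to 0.046.

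**5. Direction.** Given a switch, the period 1 test rejects a true null in 25% to 78% of trials when the imbalance favours the Test-first group, and in 0% when it favours Control-first. These rates explain the inflation in step 4; they are not an additional harm.

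**6. Secondary tests at nominal 0.0125.** 0.0166 to 0.0237 (5% trigger) and 0.0181 to 0.0238 (10%). The simulation uses one value per period, so the figure for brightness perception, whose model includes scene, is approximate.

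**7. Power without carry-over, multifocal visual range.** Overall power falls from 0.89 to 0.87–0.88 (5% trigger) or 0.85–0.86 (10%). In a trial that switches it is about 0.5, because the result follows the imbalance: 0.987 to 0.999 in one direction, 0 to 0.089 in the other. A period 1 test applied regardless of the sequence result would have power 0.62 at ρ = 0, 0.36 at 0.5 and 0.11 at 0.9.

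**The case against.** **The rule guards against carry-over.** This is the strongest defence. If carry-over exists, the two-period estimate is biased by half of it. Sizes below are in paired SDs and are assumed.
- *Carry-over favouring Test, no lens effect.* At 0.26 the error is 10–13% with the rule and 12% without; at 0.5 it is 18–33% against 34%; at 0.915 it is 10–73% against 80%. The rule gives almost no protection at the smallest size and partial protection at larger ones. Neither analysis holds the level.
- *Carry-over against Test,* as when a benefit lingers into the Control period. At 0.26, two-period power for multifocal visual range falls from 0.89 to 0.67, against 0.67–0.72 with the rule. At 0.52 it is 0.36 against 0.39–0.60. At 0.13 the two are about equal.

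So the rule can help when carry-over is substantial. That stands as a cost of deleting it, but it does not restore the level in the no-carry-over case that Section 4.2 expects.

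**Covariates may shrink the imbalance.** Section 14.5 says: "Other baseline and subject characteristics such as age, gender, race, and iris color will be included as fixed covariates when appropriate". They can lower between-subject variance, but even if they removed all of it (ρ = 0) the error would still be 3.2% or 3.5%.

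**The inflation is modest, and this is a feasibility study.** The error stays below 5% in every no-carry-over setting tried, a switch then occurs in only 5–10% of trials at a 5% or 10% trigger, and the secondary tests stay below 0.025. The exact size depends on inputs the documents do not give. All of this is fair, but the direction does not depend on those inputs, and the plan itself promises 0.025.

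**Conclusion.** The concern holds. As written, the rule does not keep the one-sided levels stated in Sections 14.2 and 14.4. With a 5% or 10% trigger, each primary test runs at 3.2% to 4.7% instead of 2.5%, and each secondary test at about 1.7% to 2.4% instead of 1.25%. This rests on normal data, equal sequences, correlation 0 to 0.9 and no carry-over. Error exceeded the stated level in every no-carry-over setting tried, including a 1% trigger and zero correlation, so the missing inputs affect only the size. The material harm is to the two primary tests; without carry-over the loss of overall power is minor. Because the rule binds the confirmatory tests and contradicts the plan's own error claim, it must be corrected before unmasking. After that, the choice of dataset would itself be open to challenge.

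**What to change.** Delete the period 1 sentence in Section 14.5 and its counterpart in Section 14.6. State that the mixed model with lens, sequence and period, fitted to both periods, is the only confirmatory test of each primary and secondary hypothesis. Report the sequence estimate with its confidence interval, and any period 1 estimate, as descriptive sensitivity results that cannot change the confirmatory conclusion.

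Without carry-over this restores 0.025 and 0.0125. The price is reliance on Section 4.2: if real carry-over exists, the two-period estimate is biased by half of it in either direction, and the study report should say so. The change needs no additional data, visits or subjects.
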